6.3 AZD3965 accountability

Accurate records of AZD3965 shipments received, capsules dispensed, and returned must be maintained. This inventory record must be available for inspection at any time by CRAs or CSMs of the CDD. AZD3965 supplies are to be used only in accordance with this protocol and under the supervision of the Investigator.

Patients will be asked to complete a patient diary to document drug administration and to return the bottle and any remaining capsules at each visit. The Investigator should make every effort to ensure patients' compliance to treatment.

The Investigator undertakes not to destroy any unused AZD3965 unless directed to by CDD staff. Any unused capsules must be destroyed according to hospital procedures and properly accounted for using the IMP Destruction Form (when instructed to do so) and also on the IMP Accountability Record. During the course of the trial the CRA will check the numbers of bottles of capsules of AZD3965 shipped to the centre, the number used and the number destroyed or returned. The pharmacy will give an account of any discrepancy.

7 INVESTIGATIONS SCHEDULE FOR PART 1 OF THE STUDY RECRUITMENT TO PART 1 OF THE STUDY IS NOW CLOSED

For details of investigations performed in Part 1 of this clinical trial, please refer to Protocol V 12.0 dated 22Aug2018 which still includes the details from this part of the trial.

8 INVESTIGATIONS SCHEDULE FOR PART 2 OF THE STUDY

In cases where a patient has investigations at a different hospital, for example weekly blood samples, then it is the Investigator's responsibility to ensure he/she receives and reviews the results in a timely manner. The results must be recorded on the eCRF and the reports from the other hospitals must be available for source data verification. Laboratory reference ranges, including effective dates, and evidence of laboratory accreditation must be obtained from all laboratories used.

8.1 **Pre-treatment evaluations**

Details of all evaluations/investigations for enrolled patients, including relevant dates, required by the protocol must be recorded in the medical records so that the eCRF can be checked against the source data.

Please also refer to the tabulated Schedule of Assessments for Part 2 of the study in Section Error! R eference source not found.

8.1.1 Obtaining written informed consent

Written informed consent must be obtained from the patient before any protocol-specific procedures are carried out.

The patient must be given adequate time to think about their commitment to the study. If more than 28 days has passed since informed consent was obtained before the start of AZD3965 dosing then the Investigator should consider whether repeat consent should be obtained from a patient.

Consent for analysis of initial historical archived or (if historical tissue not available) fresh (new) screening tumour sample for MCT1 and MCT4 IHC profiling must be obtained prior to analysis of the sample for the trial and should be obtained pre-screening or at the time of full trial consent. Analysis of the sample can occur in parallel to screening and the result does not need to be confirmed before the patient enrols onto the study.

Only the Principal Investigator (PI) and those Sub-Investigator(s) delegated responsibility by the PI, and have signed the Delegation Log, are permitted to gain informed consent from patients and sign the consent form. All signatures must be obtained before the occurrence of any medical intervention required by the protocol (ICH GCP 4.8.8 and 8.3.1.2). The patient should sign and date the consent form in the presence of the Investigator, followed by the Investigator signature. The date of the signatures of both the patient and the PI/Sub-Investigator should be the same.

The PI or the Sub-Investigator must inform the patient about the background to, and present knowledge of the normal management of their disease and the AZD3965 and must also ensure that the patient is aware of the following points.

- The known toxicity of AZD3965 and the possibility of experiencing side-effects.
- That AZD3965 is new and that the exact degree of activity is at present unknown, but that treating him/her will contribute to further knowledge.
- The potential dangers of becoming pregnant (or the patient's partner becoming pregnant) and he/she has been given information about appropriate medically approved contraception (refer to Section 10.7).
- That he/she may refuse treatment either before or at any time during the trial and that refusal to participate will involve no penalty or loss of benefits to which they are otherwise entitled.
- Whom to contact for answers to pertinent questions about the research and their rights, and also who to contact in the event of a research-related injury.

A copy of the consent form and patient information sheet must be given to the patient to keep and the original consent form and patient information sheet, must be filed in the Investigator Trial File (ITF) (unless otherwise agreed that the original consent form will be filed in the medical records and the copies kept in the ITF).

8.1.2 Pre-screening

The following should be performed/obtained within six months before the patient receives the first dose.

- Written informed consent (as detailed in Section Error! Reference source not found.).
- Confirmation that tumour samples are available and can be used for the study to confirm MCT1 and MCT 4 expression as demonstrated by IHC either during pre-screening, screening or once the patient is enrolled on the study.

All patients in Part 2 should give separate written consent before analysis of historical or fresh (new) screening tumour biopsy sample taken for MCT1 and MCT4 IHC profiling.

[figure not shown]
Historical tumour biopsy samples can be used if they were obtained more than 6 months prior to Day 1. However, it's preferred that fresh (new) samples are used to provide a more accurate result.

For those patients where a historical tumour biopsy sample is not available or the MCT1 and MCT4 IHC profiling is inconclusive and the patient hasn't yet been enrolled on to the study, a fresh (new) screening tumour biopsy will be preferred. The fresh (new) screening sample tumour biopsy must be performed/obtained **within eight weeks before** the patient receives the first dose.

8.1.3 Evaluations within four weeks prior to first dose (Day -28 to Day -1)

The following should be performed/obtained within the four weeks before the patient receives the first dose.

- Written informed consent (as detailed in Section 8.1.1);
- Demographic details;
- Medical history including prior diagnosis, prior treatment, concomitant diseases and concomitant treatment;

Radiological disease assessments: Radiological measurements (chest computerised tomography (CT) scan of neck, chest, abdomen and pelvis, FDG-PET/CT for those patients with PET-avid disease (as applicable) magnetic resonance imaging (MRI), bone scan (as applicable) – must be performed within four weeks before the patient receives the first dose.

Note that all adverse events (AEs), including serious adverse events (SAEs), must be monitored and recorded in the eCRF from the time the patient consents to any protocol-specific procedure (see Section 10 for further details).

8.1.4 Evaluations within two weeks prior to first dose (Day -14 to Day -1)

The following should be performed within the two weeks before the patient receives the first dose:

- Serum or urine human chorionic gonadotropin (HCG) test to rule out pregnancy at trial entry; results must be obtained and reviewed before the first dose of the AZD3965 is taken, if applicable (i.e. women of child bearing potential);
- Echocardiogram (ECHO);
- Ophthalmic test: Best corrected visual acuity;

• Pattern electro-retinography (pERG) and full-field electro-retinography (ffERG) (light and dark adapted) (or equivalent ERG assessment as previously agreed with the CDD).

8.1.5 Evaluations within one week prior to first dose (Day -7 to Day -1)

[figure not shown]
The following should be performed **within one week before** the patient receives the first dose:

- Clinical disease measurements, if applicable (i.e. patients with clinically assessable disease);
- Tumour serum markers (if applicable);
- Complete physical examination;
- WHO performance status;
- Weight and temperature;
- Seated blood pressure (BP) and pulse rate;
- Chest X-ray (CXR); If the baseline CT/MRI scan included the thorax, a CXR may not be necessary provided all windows are presented for review.
- Laboratory tests (blood/urine samples) to confirm eligibility (see section 4.1.1 for required values):
 - Haematology haemoglobin (Hb), white blood cells (WBC) with differential count (neutrophils, lymphocytes, monocytes, reticulocytes) and platelets
 - Biochemistry sodium, potassium, adjusted calcium, phosphate, urea, creatinine, total protein, albumin, bilirubin, alkaline phosphatase (ALP), alanine aminotransferase (ALT), aspartate aminotransferase (AST), lactate dehydrogenase (LDH), glucose (fasting at baseline to confirm eligibility and then non-fasting at subsequent timepoints. If non-fasting result is ≥7.8mmol/l fasting glucose should be repeated), lactate and bicarbonate (at baseline [screening] to confirm eligibility and Cycle 1 Day 1 only).
 - Urinalysis pH, specific gravity, glucose, protein, blood, ketones
 - Coagulation PT (screening only)
- Cardiac Troponin T or I;
- Electrocardiogram (ECG); including measurement of QTc and verified manually (QTcF correction). ECG traces must be checked by an attending physician, consultant or specialist registrar, at the time of generation. A comment confirming normal/abnormal must be added along with a signature and date on the ECG to confirm review (abnormal ECGs to be reviewed by a Cardiologist prior to patient registration);

8.2 Evaluations on Cycle 1 Day 1 (+/- 24 hours)

- Administration of first dose of AZD3965;
- Blood tests to include bicarbonate and lactate: See section 8.1.5 (blood to be taken after first dose);

8.3 Evaluations at 24 hours (± 2 hours) after the first dose of AZD3965 treatment

- Cardiac Troponin T or I; to be repeated at 48 +/-2 hours post-dose;
- ECGs (including measurement of QTc and verified manually (QTcF correction);

ECG traces must be checked by an attending physician, consultant or specialist registrar, at the time of generation. A comment confirming normal/abnormal must be added along with a signature and date on the ECG to confirm review. Abnormal ECGs to be reviewed by a Cardiologist prior to dosing;

8.4 Evaluations during continuous AZD3965 treatment Cycles 1–12 (excluding Cycle 1 Day 1)

(See Section 8.2 for Cycle 1 Day 1 and Section 8.5 for Cycle 13 onwards)

- Adverse events and concomitant treatments: At each visit an assessment of any AE experienced since the previous visit must be made by the Investigator or Research Nurse and the start and stop dates of the AE together with the relationship of the event to treatment with AZD3965 must be recorded in the medical records. All AEs must be graded according to NCI CTCAE Version 4.02. Any concomitant treatment must also be recorded in the medical records and in the eCRF (see Section 10 for further details regarding AE reporting requirements);
- Physical examination: When clinically indicated, a symptom-directed physical examination will be performed weekly during the first cycle and on the first day of each cycle in subsequent cycles (±1 day). N.B. Dermatological assessment to include questioning on genital skin changes or sores and experience of testicular pain in male patients;
- WHO performance status and weight on the first day of each cycle (±1 day);
- Temperature, seated BP and pulse rate every week in Cycle 1 and 2, and every 2 weeks thereafter (±1 day);
- Laboratory tests (blood/urine) must be repeated weekly in Cycle 1 and 2, and every 2 weeks thereafter (±1 day): see Section8.1.5;
- ECGs (include measurement of QTc and verified manually (QTcF correction)): weekly in Cycle 1 and 2, and every 2 weeks thereafter (±1 day);

ECG traces must be checked by an attending physician, consultant or specialist registrar, at the time of generation. A comment confirming normal/abnormal must be added along with a signature and date on the ECG to confirm review. Abnormal ECGs to be reviewed by a Cardiologist prior to dosing.

[figure not shown]
• Cardiac Troponin T or I: weekly in Cycle 1 and 2, and every 2 weeks thereafter (±1 day);

- Questionnaire for eye toxicity: weekly in Cycle 1 (±1 day). If the patient reports any changes in their vision, Ophthalmic tests listed in the bullet point below and ERG assessments should be performed (as per the 'Management of eye toxicity' appendix 4);
- Ophthalmic test: Best corrected visual acuity. To be conducted on the first day of each cycle (±3 days);

If a reduction or changes are identified on the ophthalmic test, ERG should be performed immediately (refer to Appendix 4 Management of eye toxicity);

- Pattern and full-field ERG (light and dark adapted) (or equivalent ERG assessment as previously agreed with the CDD) to be performed at the end of Cycle 1 ±3 days and then repeated every 28±3 days if the patient reports symptoms of eye toxicity/changes in their vision.
 ERGs can be stopped after the end of Cycle 1 if no symptoms are reported and the Ophthalmologist agrees no further ERG testing is required;
- Assessment of disease (radiological, clinical if applicable, and tumour markers): This must be repeated at the end of every 2 cycles (±3 days) unless assessment has been performed within the previous 4 weeks (28 days).

PLEASE NOTE: If patient presents with disease progression, assessment of tumour disease should be performed at the last study visit unless assessment has been performed within the previous four weeks (28 days). If assessment is to be conducted on Cycle 1 Day 29 (or Day 1 Cycle 2), assessment must be performed prior to the fresh (new) on study paired tumour biopsy.

Blood PK assays: see Section 9.

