1.4 Administration schedule

AZD3965 is available as 5, 10, 20 and 30 mg capsules and patients will take their dose orally once or twice every day (in the absence of toxicity).

One treatment cycle will consist of 28 days (with Cycle 1 including an additional dosing day at Day -7⁴ for Part 1 of the trial only).

In the Part 1 dose escalation, up to six evaluable patients were treated at each dose level with a dose on Day -7 followed by continuous daily dosing starting on Day 1 (in the absence of toxicity after the Day -7 dosing).

The starting dose was 5 mg once daily and the next total daily dose level was 10 mg.

Pharmacokinetic (PK) assessments were performed to assess the half-life and potential accumulation of the drug in order to inform whether dosing for future cohorts should be once or twice daily.

The total daily dose was doubled in successive cohorts until a Grade 2 highly probable or probably related adverse drug reaction was reported according to the National Cancer Institute Common Terminology Criteria for Adverse Events (NCI CTCAE) Version 4.02. Subsequent dose increases between cohorts were up to a maximum of 50% (to the nearest 5 mg) driven by reported safety, PK and pharmacodynamic (PD) data. However, an upper limit on dose escalation was set using PK data (see Section 2.2.9). If continuous daily dosing is not tolerated at levels that inhibit MCT1 then intermittent schedules will be explored.

Up to six evaluable patients were treated at each dose level. At least one male patient was treated in each cohort If a dose limiting toxicity (DLT) was observed then the cohort was expanded to six patients. If a second DLT was reported no further dose escalation was performed and a total daily dose level below was expanded to six patients to identify the MTD.

An interval of 14 days (from Day -7 (7 days prior to Day 1) was observed between the recruitment of the first and second patients in a cohort but the subsequent patients were treated in parallel. Twenty-eight days (from Day 1) of data (safety, PK and PD) was available for a minimum of three patients in a cohort in order to make the decision to dose escalate.

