3.2 Patient evaluability

Part 1:

All patients that met the eligibility criteria and take at least one dose of AZD3965 were evaluable for safety decisions.

[figure not shown]
Patients who received less than 75% of their first continuous treatment cycle (for reasons other than toxicity) would not be evaluable for dose escalation decisions. Patients who completed 75% of their first continuous treatment cycle but did not complete the end of Cycle 1 ERG and ophthalmology assessments could also not be evaluable for dose escalation decisions. This was discussed on a per patient basis between the Investigator, Chief Investigator (CI) and CDD.

Part 2:

All patients that meet the eligibility criteria and take at least one dose of AZD3965 will be evaluable for safety decisions.

All patients who meet the eligibility criteria and take at least 75% of their first continuous treatment cycle (28 days) of AZD3965 and have a baseline assessment of disease will be evaluable for response.

To be assigned a status of complete response (CR) or partial response (PR), changes in tumour measurements must be confirmed by repeat measurements performed no less than four weeks after the response criteria are met. To be assigned a status of stable disease (SD), follow-up measurements must have met the SD criteria at least once and at least six weeks after the initial dose of the IMP AZD3965 is given.

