8.5 Evaluations from Cycle 13 onwards

From Cycle 13 onwards, the patient will attend the study site on Day 1 of each cycle. A telephone call or on-site visit on Day 15 will be conducted if deemed required (either by site staff or by the patient).

PLEASE NOTE: Abnormal or out of range laboratory results from tests carried out on Day 1 will require an onsite visit or telephone call on Day 15 to ensure continuing patient safety and well-being is reviewed during the treatment cycle.

The frequency of the following investigations may be adjusted (increased or decreased) if clinically indicated or deemed required by the Investigator.

At each study visit:

- Adverse events and concomitant treatments: At each visit an assessment of any AE experienced since the previous visit must be made by the Investigator or Research Nurse and the start and stop dates of the AE together with the relationship of the event to treatment with AZD3965 must be recorded in the medical records. All AEs must be graded according to NCI CTCAE Version 4.02. Any concomitant treatment must also be recorded in the medical records and in the eCRF (see Section 10 for further details regarding AE reporting requirements).
- AE assessments must include any visual changes which should be managed as per Section 10.

On the first day of each cycle (±1 day):

- Physical examination: When clinically indicated or deemed required by the Investigator, a symptom-directed physical examination will be performed. N.B. Dermatological assessment to include questioning on genital skin changes or sores and experience of testicular pain in male patients.
- WHO performance status and weight.
- Temperature, seated BP and pulse rate. May be conducted at Cycle Day 15 (±1 day) if onsite visit.
- Laboratory tests (blood/urine); see Section 8.1.5. May be conducted at Cycle Day 15 (±1 day) if onsite visit.

Every 3 cycles (±3 days):

• Assessment of disease (radiological, clinical – if applicable, and tumour markers): This must be repeated at the end of every 3 cycles (±3 days) unless assessment has been performed within the previous 4 weeks (28 days).

PLEASE NOTE: If patient presents with disease progression, assessment of tumour disease should be performed at the last study visit unless assessment has been performed within the previous four weeks (28 days).

• Opthalmic test: Best corrected visual acuity. To be conducted on the first day of every third cycle (±3 days).

[figure not shown]

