11.2.2 Evaluations during and at Off-study visit

Tumour assessments must be repeated every 2 cycles/8 weeks (Cycles 1-12) and every 3 cycles/ 12 weeks (Cycle 13 onwards) or more frequently, when clinically indicated. All lesions measured at baseline must be measured at every subsequent disease assessment and recorded clearly on the scan reports. All non-measurable lesions noted at baseline must be noted on the scan report as present or absent.

All patients, who are removed from the trial for reasons other than progressive disease, must be re-evaluated at the time of treatment discontinuation, unless a tumour assessment was performed within the previous four weeks.

It is the responsibility of the Principal Investigator to ensure that the radiologists are aware of the requirement to follow-up and measure every target lesion mentioned at baseline and comment on the non-target lesions in accordance with RECIST criteria or the IWG criteria for lymphoma (Appendix 2A and 2B).

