2.4.3. Best overall response: all time points

The best overall response is determined once all the data for the patient is known.

Best response determination in trials where confirmation of complete or partial response IS NOT required:

Best response in these trials is defined as the best response across all time points (for example, a patient who has SD at first assessment, PR at second assessment, and PD on last assessment has a best overall response of PR). When SD is believed to be best response, it must also meet the protocol specified minimum time from baseline. If the minimum time is not met when SD is otherwise the best time point response, the patient's best response depends on the subsequent assessments. For example, a patient who has SD at first assessment, PD at second and does not meet minimum duration for SD, will have a best response of PD. The same patient lost to follow-up after the first SD assessment would be considered inevaluable. A 'positive' FDG-PET scan lesion means one which is FDG avid with an uptake greater than twice that of the surrounding tissue on the attenuation corrected image.

Target lesions	Non-target lesions	New lesions	Overall response
CR	CR	No	CR
CR	Non-CR/non-PD	No	PR
CR	Not evaluated	No	PR
PR	Non-PD or not all evaluated	No	PR
SD	Non-PD or not all evaluated	No	SD
Not all evaluated	Non-PD	No	NE
PD	Any	Yes or No	PD
Any	PD	Yes or No	PD

Table 1 – Time point response: patients with target (+/–non-target) disease

Any	Any	Yes	PD	

CR = complete response, PR = partial response, SD = stable disease, PD = progressive disease, and NE = inevaluable.

Table 2 – Time point response: patients with non-target disease only

Non-target lesions	New lesions	Overall response
CR Non-CR/non-PD Not all evaluated Unequivocal PD Any	No No Yes or No Yes	CR Non-CR/non-PD(a) NE PD PD

CR = complete response, PD = progressive disease, and NE = inevaluable.

(a) 'Non-CR/non-PD' is preferred over 'stable disease' for non-target disease since SD is increasingly used as endpoint for assessment of efficacy in some trials so to assign this category when no lesions can be measured is not advised.

Best response determination in trials where confirmation of complete or partial response is required: Complete or partial responses may be claimed only if the criteria for each are met at a subsequent time point as specified in the protocol (generally 4 weeks later). In this circumstance, the best overall response can be interpreted as in Table 3.

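### The 28-day waiver in Section 8.4 lets a scan too early to support stable disease replace the end-of-Cycle-2 assessment, and conflicts with Section 11.2.2 and the Section 8.8 table

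*Protocol*

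**What the plan says.** Four places in the protocol bear on the timing of Part 2 disease assessment.

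- **Section 8.4 (Cycles 1–12):** disease assessment is to be "repeated at the end of every 2 cycles (±3 days) unless assessment has been performed within the previous 4 weeks (28 days"). The exception has a 28-day look-back but no earliest date for the earlier scan. A note under the same bullet reads "If assessment is to be conducted on Cycle 1 Day 29 (or Day 1 Cycle 2), assessment must be performed prior to" the on-study paired biopsy, so a scan at about four weeks is foreseen.
- **Sections 3.2 and 11.3:** for a patient to be assigned SD, "follow-up measurements must have met the SD criteria at least once and at least six weeks after the initial dose" of AZD3965.
- **Section 11.2.2:** "Tumour assessments must be repeated every 2 cycles/8 weeks (Cycles 1-12) and every 3 cycles/ 12 weeks (Cycle 13 onwards) or more frequently" where there is clinical reason. Its only four-week exception is for patients removed from the trial for reasons other than progression.
- **Section 8.8 table:** the radiology row asks for a scan at the end of every two cycles. Footnote (o), the 28-day exception, is attached only to the off-study cell of that row.

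Section 8.5 uses the Section 8.4 wording on a three-cycle schedule: "repeated at the end of every 3 cycles (±3 days) unless assessment has been performed within the previous 4 weeks (28 days").

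**The concern.** The look-back in Section 8.4 and the minimum time for SD were not set against each other. The look-back reaches to about four weeks after first dose, whereas SD needs six. In between is a band of days on which a scan is late enough to lift the Week 8 requirement but too early to count towards SD. The Cycle 1 Day 29 assessment falls in that band on the nominal calendar.

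Sections 1.2.2 and 3.1.2 name SD as part of the Part 2 objective-response endpoint, and Section 14.5 lists best response and time to progression for each patient. The Week 8 scan is the only one scheduled before Week 16 that can support SD. If it is not taken, no later analysis can recover it.

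Sites also receive two instructions. One following Section 8.4 may omit a scan that one following Section 11.2.2 or the Section 8.8 table must take.

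**Working it through.** **Inputs**

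- Cycle length, Section 1.4: "One treatment cycle will consist of 28 days". First dose is Day 1, so protocol Day *d* is *d* − 1 days after first dose.
- Look-back of 28 days and a due-date window of ±3 days, Section 8.4.
- SD minimum of six weeks (42 days) from first dose, Sections 3.2 and 11.3.

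**The plan's own interval.** 2 × 28 = 56 days = 8 weeks, which agrees with Section 11.2.2. End of Cycle 2 is Day 56 (window 53–59). End of Cycle 4 is Day 112 (window 109–115).

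**Earliest scan that lifts the requirement.** Due day minus 28: 56 − 28 = Day 28. Across the window this is Day 25 (53 − 28) to Day 31 (59 − 28).

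**Earliest scan that can support SD.** *d* − 1 ≥ 42 gives Day 43.

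**The gap between the two rules.** On the nominal due date, scans on Days 28–42 lift the Week 8 requirement but cannot support SD. With the window, the band starts between Day 25 and Day 31 and always ends at Day 42.

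**Time to the next scan scheduled under Section 8.4** (112 − *d*):

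| Waiving scan | Days after first dose | Can support SD | Days to Day 112 | Weeks |
|---|---|---|---|---|
| Day 28 | 27 | no | 84 | 12.0 |
| Day 29 | 28 | no | 83 | 11.9 |
| Day 35 | 34 | no | 77 | 11.0 |
| Day 42 | 41 | no | 70 | 10.0 |
| Day 43 | 42 | yes | 69 | 9.9 |

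The nominal gap is therefore 10 to 12 weeks against 8. With ±3 days on the later scan it runs from 67 days (109 − 42, 9.6 weeks) to 87 days (115 − 28, 12.4 weeks). If the eight-week interval were instead restarted from a Day 29 scan, the next would fall on Day 85 (29 + 56), and Week 8 would still be missed.

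**Delay in dating progression.** Progression visible at Day 56 but first imaged at Day 112 is dated 112 − 56 = 56 days, or 8 weeks, late.

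**Cycle 13 onwards.** A scan 8 weeks after the last one lifts the 12-week scan. The next is due at 24 weeks, a gap of up to 24 − 8 = 16 weeks.

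**After the fix.** Patients still on treatment are scanned on Days 53–59, which is 52–58 days (7.4–8.3 weeks) after first dose. That meets the six-week minimum, and the following interval returns to about eight weeks.

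**The case against.** Much of the case on the other side stands and limits the point.

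- A reader might infer that a patient scanned on Days 28–42 can never be classed as SD. The text does not say so. SD must be met once at six weeks or later, so an end-of-Cycle-4, off-study, discontinuation or extra clinically prompted scan can establish it.
- A reader might infer that Section 8.4 forbids the Week 8 scan. It only lifts an obligation, and a site honouring Section 11.2.2 as well would still scan.
- The bullet covers radiological, clinical and marker assessment together. Its natural reading is that this assessment was already done, not that any partial one suffices.
- No Day 29 scan appears in the visible table, and text around it is removed. With the ±3-day window, a Day 29 scan is 29 or 30 days old if the assessment is due on Day 58 or 59, and then waives nothing.
- Late dating applies to clinically silent progression. Section 11.2.2 allows extra scans when there is clinical reason, and Sections 8.4, 8.6 and 11.2.2 call for assessment at progression, off-study or discontinuation unless one is recent.
- A reader might suppose that early scans reflect clinical worry, making the error systematic. Nothing in the protocol says so, and the one documented route is tied to a biopsy.
- A reader might also take the Appendix 2A example of SD followed by progression as fixing the outcome at progressive disease. It belongs to trials without response confirmation, whereas this trial requires confirmation. It is also solid-tumour text, and Appendix 2B covers lymphoma.
- From Cycle 13 the six-week minimum is long past, and Section 8.5 lets the investigator change the frequency.

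What remains is that Section 8.4, followed as written, can remove the Week 8 scan on the strength of one that cannot support SD, and that it disagrees with Section 11.2.2 and the Section 8.8 table. The option of an extra scan does not restore a required one.

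**Conclusion.** The point holds in limited form. On the nominal calendar, a scan on Days 28–42 lifts the end-of-Cycle-2 requirement without being able to support SD, and leaves 10 to 12 weeks to the next scan scheduled under Section 8.4 (83 days from Day 29). Two effects follow: SD cannot be assigned to a patient truly stable at Week 8 who progresses or leaves before a qualifying scan, and clinically silent progression at Week 8 may be dated up to about eight weeks late.

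This assumes that a site relies on Section 8.4 alone, that the earlier scan falls in the band, and that no extra scan is taken. The protocol gives no frequency for any of these, so the number of patients affected is unknown. For scale only, one of 20 evaluable patients is 1/20 = 5 percentage points, but the protocol specifies no SD rate. Anti-tumour activity is a secondary objective and is reported descriptively. The matter ranks between a minor correction and one that should be made. The contradiction between sections needs reconciling however few patients it touches.

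**What to change.** Reconcile Section 8.4 with Section 11.2.2 and the Section 8.8 table. The simplest change is to delete the 28-day exception from the on-treatment disease-assessment bullet in Section 8.4, so that unscheduled scans add to the scheduled ones. If an exception is wanted, state at least that a scan less than six weeks after first dose does not replace the end-of-Cycle-2 assessment, and carry the same exception into Section 11.2.2 and the table. Align the matching bullet in Section 8.5 for consistency. The exception for the off-study assessment can stay.

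The cost is a short wording amendment and at most one scan per affected patient, which Section 11.2.2 already requires.
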